### 7.2

### Mavenclad® (Cladribine Tablets)

Over recent years, there has been an increase in the number of available disease-modifying therapies (DMT) for treatment of MS (Wingerchuk 2014). Despite the recent approvals of such therapies, the treatment burden of MS remains significant. New treatment options are still required to reduce the number of relapses and disease progression that patients experience (Hadjigeorgiou 2013, Tramacere 2015, Tsivgoulis 2015, Lucchetta 2020).

Mavenclad® (cladribine tablets) is approved (European Medicines Agency approval on 25 August 2017) for the treatment of highly-active relapsing MS in adults. These tablets involve a synthetic deoxyadenosine analogue that acts in peripheral tissues and enters the CNS, where it is taken up by lymphocytes and phosphorylated by deoxycytidine kinase. This results in targeted and sustained reductions of the T and B lymphocytes that are implicated in the pathogenesis of MS (Leist 2011).

It has been demonstrated that treatment with cladribine tablets in 2 short courses over 2 consecutive years has consistently shown robust clinically and statistically significant benefits in patients across the spectrum of relapsing MS (early to late stages, treatment naïve or experienced patients) (Giovannoni 2010, Leist 2011). The recommended cumulative dose of cladribine tablets is 3.5 mg/kg body weight over 2 years, administered as 1 treatment course of 1.75 mg/kg per year. Each treatment course consists of 2 treatment weeks, one at the beginning of the first month and one at the beginning of the second month of the respective year. Detailed information on the chemistry, pharmacology, efficacy, and safety of cladribine tablets is provided in the Summary of Product Characteristics (SmPC). Overall, the most common, clinically relevant adverse reactions

reported among patients treated with cladribine tablets in clinical studies are lymphopenia and herpes zoster.

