9.8 Exposure time

Duration of exposure = date of last dose of cladribine – date of first dose of cladribine +1.

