9.9 Follow-up time

Follow-up period is defined as follows:

- Follow-up: from date of last dose of cladribine until date of last contact (see Section 9.5).

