Adverse events	Incomplete AE-related dates will be imputed as follows: 
• In case the onset date is partially missing but the onset month and year, or the onset year are equal to cladribine initiation then the onset date will be imputed by the minimum of cladribine initiation date and AE resolution date (if not missing).• In all other cases, the missing onset day or missing onset month will be imputed by 1.• Incomplete stop dates will be imputed by the last day of the month (if day is missing only), if not resulting in a date later than the date of participant's death. In the latter case, the date of death will be used to impute the incomplete stop date.• In all other cases, the incomplete stop date will not be imputed.
Previous and concomitant medication (including prior/subsequent DMTs)	Incomplete prior/concomitant medication (and DMT) start and stop dates will be imputed as follows: 
• If the medication start date is missing completely, then the medication start date will be replaced by the cladribine initiation date.• If the day of medication start date is missing, but the month and year are equal to the cladribine initiation date, then the medication start date will be replaced by the cladribine initiation date. For example, if the medication start date is --/JAN/2015, and cladribine initiation date is 15/JAN/2015, then the imputed medication start date will be 15/JAN/2015.• If both the day and month of medication start date are missing but the start year is equal to the cladribine initiation date, then the medication start date will be replaced by the cladribine initiation date. For example, if the medication start date is --/---/2014, and cladribine initiation date is

	
19/NOV/2014, then the imputed medication start date will be 19/NOV/2014.
 
• In all other cases the missing medication day or missing medication month will be replaced by 1. Incomplete stop date will be replaced by the last day of the month (if day is missing only), if not resulting in a date later than the date of participant's death. In the latter case the date of death will be used to impute the incomplete stop date.• In all other cases the incomplete medication stop date will not be imputed. 
In case an imputed medication start date is later than the medication stop date, it will be replaced by the medication stop date.

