Dates of cladribine	
Start date of cladribine :
 
• If the day is missing and the month and year are available, the missing day will be imputed to the 15th of the month.• If both the month and day are missing and the year is available, and the end date is available for cladribine treatment Year 1 Week 2, cladribine initiation date will be imputed to the first day of the month prior to the date of Year 1 Week 2. For example, if the end date of week 2 is --/FEB/2019, the cladribine initiation date will be 01/JAN/2019. 
End date of cladribine :
 
• If the last date of cladribine is completely missing and no death date the participant should be considered to be ongoing and use the cut-off date for the analysis as the last dosing date• If the last date of cladribine is partially missing, then imputed last dose date is: = Last day of the month, if both Year and Month are available and Year = Year of min (discontinuation date, death date) and Month < the month of min (discontinuation date, death date)

10 Study Participants

The subsections in this section include specifications for reporting participant disposition and study discontinuations. Additionally, procedures for reporting protocol deviations are provided.

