- T1DMT (years): (Date of start of first subsequent DMT - last cladribine administration date + 1)/365.25.

Patients who did not start any subsequent DMT will be censored at the date of last contact.

The T1DMT will be summarised using the total number and % of patients with an event. The number and % of censored patients will be also presented.

The T1DMT and associated 95% CI will be summarised at yearly intervals using the KM method, the median TSDMT and corresponding 95% CI (whenever estimable) will be also included. KM curves will be provided.

Time to second subsequent DMT (T2DMT) will be derived as follows:

- T2DMT (years): (Date of start of second subsequent DMT - last cladribine administration date + 1)/365.25.

The T2DMT will be summarised in the same way of T1DMT only if at least 5% of patients have a second subsequent DMT recorded.

14.2.4 *Secondary Objective: Derivation and analysis of the secondary outcome: EDSS and disability progression*

The Annual EDSS results at cladribine initiation and at Year 2 and the corresponding change from baseline (i.e. cladribine initiation) will be summarised using descriptive statistics. Scores will be derived from the 'Annual EDSS scores' CRF page. All other assessment will be presented in a listing.

The number and % of patients with disability progression confirmed over 6 months at Year 2 after cladribine initiation will be also summarised.

EDSS progression is defined as an increase in the EDSS scale as follows:

- If the EDSS score at cladribine tablet initiation is 0, the increase must be ≥ 1.5 units
- If the EDSS score at cladribine tablet initiation is ≥ 0.5 or ≤ 4.5 , the increase must be ≥ 1.0 units
- If the EDSS score at cladribine tablet initiation is ≥ 5.0 , the increase must be ≥ 0.5 units.

EDSS assessments will be assigned to time windows as defined in Section 9.6.

15 Safety Analyses

Safety analyses will be performed based on the FAS by the most recent prior DMT and overall.

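### SAP 9.10 sets a completely missing last cladribine date to the analysis cut-off, and a completely missing subsequent-DMT start to the initiation date, so times to next DMT become negative or are lost

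*SAP*

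**What the plan says.** SAP 9.10, under dates of cladribine: "If the last date of cladribine is completely missing and no death date the participant should be considered to be ongoing", and the analyst is told to "use the cut-off date for the analysis as the last dosing date".

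The row of the same table for medications, which expressly includes prior and subsequent DMTs, says: "If the medication start date is missing completely, then the medication start date will be replaced by the cladribine initiation date".

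The last cladribine date then enters four derivations:
- SAP 9.8: "Duration of exposure = date of last dose of cladribine" minus the first-dose date, plus 1.
- SAP 9.9: follow-up runs "from date of last dose of cladribine until date of last contact".
- SAP 14.2.3: "T1DMT (years): (Date of start of first subsequent DMT - last cladribine administration date + 1)/365.25". T2DMT has the same origin, and patients without a subsequent DMT are censored at last contact.
- SAP 14.2.2: for a patient who did not complete the full course, the discontinuation date is the earliest DMT start after the last cladribine administration. If there is none, it is the last administration date itself.

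Protocol 7.2 describes "treatment with cladribine tablets in 2 short courses over 2 consecutive years". Protocol 9.2.2 describes treatment weeks of 4 or 5 days, with the Year 2 course starting no later than 18 months after initiation. SAP 13 allows for further courses in Years 3 to 5.

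**The concern.** Treating a missing end date as ongoing use suits a drug taken continuously. Here dosing falls in a few short weeks, and even a Year 3 to 5 course is a separate course. A blank last date therefore almost never means dosing up to the cut-off. It means that the chart or the eCRF lacks the date.

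The imputed date becomes time zero for T1DMT and T2DMT, which are listed endpoints of a secondary objective (SAP 5). If time zero moves to the end of observation, every earlier event falls before it. The DMT-start rule produces the same reversal from the other side, because it moves the event back to Day 1. SAP 9.10 checks the order of an imputed medication start only against that medication's own stop date. No check, floor or exclusion compares it with the last cladribine dose.

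**Working it through.** **Observation window (the plan's own figure).** Protocol 9.2.3 gives 5 to 7 years, counted from one year before initiation.
- Minimum: 1 + 3 (initiation to enrolment) + 1 (to the second chart review) = 5 years.
- Maximum: 1 + (Q3 2023 minus 22 August 2017) = 6.86 to 7.11 years.

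Both agree with the protocol. Without the pre-treatment year, observation ends 4 to 6 years after initiation. The SAP gives no calendar cut-off, so I use study days 1461, 1826 and 2192 for years 4, 5 and 6.

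**Assumed last-dose days, from the described course timing.**
- Day 35: Year 1 course only.
- Day 400: Year 2 on time (365 + 35).
- Day 583: Year 2 delayed by 6 months (548 + 35).
- Day 1131: a further course at the start of Year 4 (1096 + 35).

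**Rule 1: last dose set to cut-off.** T1DMT = (DMT start - last dose + 1)/365.25. This is below zero whenever the DMT starts two or more days before the cut-off. For a DMT started at year 3 (day 1096):

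| Last dose used | Calculation | T1DMT (years) |
|---|---|---|
| Day 400 | (1096 - 400 + 1)/365.25 | +1.91 |
| Cut-off, year 4 | (1096 - 1461 + 1)/365.25 | -1.00 |
| Cut-off, year 5 | (1096 - 1826 + 1)/365.25 | -2.00 |
| Cut-off, year 6 | (1096 - 2192 + 1)/365.25 | -3.00 |

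**Rule 1, non-switchers.** They are censored at last contact, which under SAP 9.5 cannot fall after the cut-off. A fully imputed date does not count towards last contact either. At best the time is 1/365.25 = +0.003 years. With last contact 180 days before cut-off it is (-180 + 1)/365.25 = -0.49 years.

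**Rule 1, discontinuation date (14.2.2).** With the last dose at cut-off, no observed DMT start can follow it. For a patient who did not complete treatment, a real switch is passed over and the date falls back to the missing administration date.

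**Rule 2: completely missing DMT start set to Day 1, last dose known.**
- Last dose day 35: (1 - 35 + 1)/365.25 = -0.09 years.
- Last dose day 400: (1 - 400 + 1)/365.25 = -1.09 years.
- Last dose day 583: (1 - 583 + 1)/365.25 = -1.59 years.

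If both dates are missing, the result is -3.99 to -6.00 years.

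**Partial DMT starts.** A missing month and day generally become 1 January. Take initiation on 1 June 2018 and a last dose on day 400 (5 July 2019). A DMT start recorded only as 2019 becomes 1 January 2019, and T1DMT is (-185 + 1)/365.25 = -0.50 years.

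**Exposure (9.8).** Excess = (cut-off day - true last-dose day)/365.25, for a cut-off at year 4 to 6.

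| True last dose | Excess exposure (years) |
|---|---|
| Day 35 | 3.9 to 5.9 |
| Day 400 | 2.9 to 4.9 |
| Day 583 | 2.4 to 4.4 |
| Day 1131 | 0.9 to 2.9 |

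**The case against.** The strongest reply concerns reach. Rule 1 applies only when the last date is completely missing; SAP 9.10 handles a partly missing date separately. Completing both Year 1 weeks is an inclusion criterion, course initiation dates are a collected variable, dosing is summarised by week, and missing data are queried (Protocol 9.2.1.1, 9.3, 9.4; SAP 13). Few patients, perhaps none, may be affected, and the study is descriptive. All of this stands. It limits the size of the problem but does not make the rules correct.

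Three stronger readings are tempting, and the documents do not support them.
- A reader might infer that the exposure tables are inflated by years. The 9.8 variable would be wrong, but SAP 13 lists tablets, delayed or missing doses and completed courses, not duration. No listed table uses the 9.9 follow-up time either.
- A reader might infer that switchers disappear from the whole subsequent-DMT analysis. The counts by preferred name in 14.2.3 come from the DMT eCRF page and do not use the last-dose date. The exposed outputs are the Kaplan-Meier results for T1DMT and T2DMT, and the SAP does not say how negative times would be handled there.
- A reader might infer that the main results are biased. The annualised relapse rate, the relapse-free analysis and the treatment-emergent AE window do not use the last-dose date (SAP 9.7, 14.1.1, 14.2.1, 15.1).

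For Rule 2, a DMT moved to Day 1 might be treated as not subsequent, which avoids a negative time. The SAP does not settle this, and the switch would then be lost or misclassified.

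**Conclusion.** Both rules are wrong as written, and the point is minor. Under the SAP's own formulas, every patient caught by Rule 1 has an unusable T1DMT. It is negative for a DMT started two or more days before cut-off, and about zero or negative for a non-switcher. In the year 3 example the error is about 3 to 5 years (from +1.9 to between -1 and -3). Rule 2 gives about -0.1 to -1.6 years, or loses the DMT.

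The sizes rest on the assumed last-dose days and a cut-off 4 to 6 years after initiation. The sign for a Rule 1 switcher needs no last-dose assumption. The documents give no frequency of missing dates, so no effect on a summary estimate can be stated. With a minimum of 90 patients in four prior-DMT subgroups, a few such records could still distort a subgroup's curve.

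**What to change.** In SAP 9.10:
- Delete the cut-off rule. Impute a completely missing last cladribine date from the last documented treatment week or course, including Year 3 to 5 courses recorded on the DMT eCRF page. If nothing is documented, leave it missing.
- For DMTs recorded as subsequent, leave a completely missing start unimputed. Do not let a partially imputed start fall before the last cladribine date.

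In SAP 14.2.3, keep all these patients in the subsequent-DMT counts, exclude them from T1DMT and T2DMT only when a date cannot be derived, and report how many are excluded.

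The cost is a few lines of text and programming. A few patients will have a missing time where they now have an imputed one, so some switchers still drop out of the Kaplan-Meier estimates. They will be counted and reported, and no patient will carry a time known to be wrong.

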10.1 Disposition of Participants and Discontinuations

The following will be presented in a summary table by the most recent prior DMT and overall:

- Total number of participants screened

- Number of screened participants who discontinued from the study after screening will be summarised overall and grouped by the main reason for discontinuation:
 - Participant did not meet all eligibility criteria
 - Withdrew consent
 - Other
- Number of enrolled participants
- Number of patients in the Full analysis set (FAS)
- Number of patients in the FAS who completed study
- Number of patients by timing of the second chart review: The second chart review should be approximately 1 year from enrolment (365 calendar days \pm 14 calendar days).
 - Within the protocol-defined window
 - Outside the protocol-defined window
- Number of patients in the FAS who discontinued the study, with the primary reason of discontinuation:
 - AE
 - Death
 - Withdrawal by subject
 - Enrolment in an investigational clinical trial during the study period
 - Other [(COVID-19-related and COVID-19-non-related)]

Listings of discontinued participants will be provided. A listing of participants affected by the COVID-19-related study disruption by unique participant identifier will also be provided.

10.2 Protocol Deviations / Exclusion from Analysis Sets

10.2.1 Important Protocol Deviations

Important protocol deviations (IPDs) are protocol deviations that might significantly affect the completeness, accuracy, and/or reliability of the study data or that might significantly affect a participant's rights, safety, or well-being. Since this is a non-interventional study and all procedures will be performed as per clinical practice, deviation from the expected schedule of assessments are not considered IPDs.

Protocol deviations will be collected from sites according to the study Protocol Deviation Plan version 1.0 from 21 July 2021. A frequency table with all protocol deviations based on FAS will be presented.

11 Demographics and Other Baseline Characteristics

Demographics and baseline characteristics will be presented for the FAS by the most recent prior DMT and overall.

11.1 Demographics

Demographic characteristics and physical measurements will be summarised descriptively using the following information from the demographic eCRF page:

- Sex (male, female)
- Age at time of informed consent (years)
- Height (cm, inches, unknown)
- Weight (kg, pounds, unknown)

Specifications for computation:

In case age is not collected in eCRF it will be derived as follows:

- Age (years) = (Informed consent year - year of birth)

In case height is recorded in inches it will be converted in cm as follows:

- Height (cm) = height (inches) x 2.54

In case weight is recorded in pounds it will be converted in kg as follows:

- Weight (kg) = weight (pounds) x 0.453592

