#### **9.2.1.1                            Inclusion Criteria**

For inclusion in the study, all of the following inclusion criteria must be fulfilled:

1. At least 18 years of age at cladribine tablet treatment initiation
2. Physician diagnosis of HDA-RRMS as defined by clinical or radiological features
3. Treatment initiation with cladribine tablet monotherapy on or after 22 August 2017 and at least 3 years before enrolment
4. Completion of Year 1 treatment of cladribine tablets (Week 1 and Week 2 treatment, per recommended dose in Year 1: 1.75 mg/kg body weight, cumulatively)
5. Provide written informed consent to participate in the study

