## **9.3 Variables**

- Demographic data at cladribine tablet initiation: Gender, age, height and weight measurements on or nearest to the date of initiating cladribine tablets in the year prior to treatment initiation
- Medical history and comorbidities at cladribine tablet initiation: All relevant medical history and comorbidities in the year prior to initiation with cladribine tablets (both past and ongoing comorbidities at date of initiation with cladribine tablets will be collected)
- Medication history at cladribine tablet initiation: Relevant medications taken in the year prior to initiation with cladribine tablets
- MS disease history: Date of initial MS diagnosis and type of MS at cladribine tablet initiation
- Prior DMTs: Any DMT for MS, taken since initial MS diagnosis and prior to initiating treatment with cladribine tablets, including starting date, end date, and dosage. The most recent DMT taken prior to initiation with cladribine tablets will be categorised in subgroups, as defined in [Section 9.7.1.1](#):
  - naïve to DMT
  - prior platform therapy
  - prior high-efficacy cell-depleting treatment

- prior high-efficacy non-depleting treatment
- Treatment with cladribine tablets: date of initiation of each treatment course, dose, potential date of discontinuation of treatment and reason for discontinuation, if applicable.
- Subsequent DMTs: Other DMTs for MS initiated after treatment with cladribine tablets will be recorded, including the date of initiation, potential discontinuation date, and dosage.
- COVID-19 vaccines: Vaccines for coronavirus disease 2019 (COVID-19) attributable to severe acute respiratory syndrome coronavirus 2 (SARS-CoV-2) administered in the years after initiation of cladribine tablets (until end of observation period) will be recorded.
- Course of disease:
  - clinician confirmed relapses: Each relapse that occurred in the year prior to treatment initiation with cladribine tablets and each year after will be recorded with the onset date (at least month and year)
  - annual EDSS scores: At start of cladribine tablet treatment Year 1, at the start of cladribine tablet treatment Year 2, and 2 years after cladribine tablet treatment initiation
  - MRI data (upon availability): T1 gadolinium enhancing lesions, T2 lesions (new/enlarging compared to a previous scan)
- Lymphocyte levels: At initiation of cladribine tablet treatment and during the years after, where available.

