9.3 Definition of Duration and ‘Time Since’ Variables

Durations in days will be calculated by the difference of start and stop date + 1 (e.g. duration of diagnosis at cladribine initiation (days) = date of MS diagnosis – date of cladribine initiation + 1) if not otherwise specified.

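### The SAP's baseline table reports age at informed consent, 3 to about 5 years after the cladribine initiation date at which the protocol defines age

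*SAP*

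**What the plan says.** **Protocol.** Section 9.3 sets the reference time for the demographic variables: "Demographic data at cladribine tablet initiation: Gender, age, height and weight measurements on or nearest to the date of initiating cladribine tablets". The abstract gives the same anchor, and so does the age criterion in section 9.2.1.1: "At least 18 years of age at cladribine tablet treatment initiation".

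**SAP.** Section 9 makes the cladribine initiation date the index date that separates baseline from the on-treatment period, and section 9.2 makes it Day 1. Section 11 states: "Demographics and baseline characteristics will be presented for the FAS by the most recent prior DMT and overall". Within that section, 11.1 lists the age variable as "Age at time of informed consent (years"). If age was not entered in the eCRF, it is derived as "Informed consent year - year of birth". Section 7 reports no change from the analyses planned in the protocol.

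**Related text.** SAP 9.3 illustrates its rule for durations with time since diagnosis at initiation, written as "date of MS diagnosis – date of cladribine initiation + 1".

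**The concern.** In many studies consent and treatment start lie days apart, and the choice between them hardly matters. Here patients are enrolled years after they started treatment, so the two dates are far apart by design. A baseline table should describe patients at the index date, and the protocol says that it will.

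Three things are at stake, all descriptive:

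- The shift has the same sign for every patient, so a larger sample does not reduce it.
- The table would mix time points: age at consent beside height and weight from the year before initiation or its date.
- The size of the shift differs between patients. The table is split by most recent prior DMT, so if the subgroups differ in the interval from initiation to consent, their ages are displaced by different amounts.

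The study has no comparator and is descriptive (protocol 9.5). Protocol 7.3 stresses that patients treated after marketing differ from those in the pivotal trial. An accurate account of who was treated is therefore one of its main products.

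**Working it through.** **Inputs**

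- Enrolment date = date of signing consent (protocol 9.1.1).
- Initiation on or after 22 August 2017 and at least 3 years before enrolment (protocol 9.2.1.1).
- Observation period, from 1 year before initiation to the second chart review: 5 to 7 years (protocol 9.2.3).
- Second chart review about 1 year after enrolment (protocol 9.2.4).
- Data collection from Q3 2021 to Q3 2023 (protocol section 6).

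**Step 1: reproduce the stated observation period.** Minimum = 1 year before initiation + 3 years to consent + 1 year to the second review = 5 years, as stated.

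**Step 2: gap between initiation and consent.** Gap = observation period − 1 − 1.

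- Minimum: 5 − 1 − 1 = 3 years.
- Maximum: 7 − 1 − 1 = 5 years.
- Calendar check on the maximum: 22 August 2017 to 30 September 2022 (one year before the end of Q3 2023) is 5.1 years.

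On an exact scale, age at consent minus age at initiation equals this gap: 3 to about 5 years for every eligible patient.

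**Step 3: the same gap in completed years.** 300,000 eligible date sets were simulated. The assumptions were initiation spread evenly from 22 August 2017 to 30 September 2019, and consent spread evenly from the later of 1 July 2021 and initiation + 3 years up to 30 September 2022.

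| Overstatement (completed years) | Date sets |
|---|---|
| 3 | 141,865 |
| 4 | 132,427 |
| 5 | 25,682 |
| 6 | 26 |

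It was never below 3. The split between rows depends on the assumed spread of dates; the lower limit follows from eligibility alone.

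**Step 4: the fallback derivation.** Consent year minus birth year ignores birthdays. In the same simulation it exceeded completed age at initiation by 3 to 6 years, and exact age at initiation by 2.0 to 5.4 years. Rounding blurs individual values but does not remove the shift.

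**Step 5: possible distortion between subgroups.** If one subgroup had the shortest gap throughout and another the longest, the artificial difference in mean age would be 5 − 3 = 2 years. That is an outer limit. The documents give no initiation dates by subgroup.

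**Step 6: the example in SAP 9.3.** Take diagnosis on 15 June 2010 and initiation on 1 March 2018, which are 2,816 days apart.

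- As written: −2,816 + 1 = −2,815 days.
- Reversed: 2,816 + 1 = 2,817 days (7.71 years).

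The formula as written gives +1 for a diagnosis on the day of initiation, 0 for the day before, and a negative value for anything earlier. Dropping the minus sign would leave the result 2 days short, so the subtraction itself has to be turned round.

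**The case against.** The best defence is that the row is labelled as age at consent, so a careful reader is told what it is, and that no outcome, subgroup or model in the SAP uses age. Both points are true. They limit the consequence, but they do not reconcile the SAP with the protocol, and the label does not supply the age at initiation that the protocol specifies.

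A reader might infer more than the documents support:

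- *That a patient under 18 at initiation could enter the analysis as an adult.* The demographics table is not the eligibility check. Eligibility is reviewed at the first chart review (protocol Table 1), the enrolled set admits only patients who met the criteria and the FAS is drawn from it (SAP 8.1), and failures are counted in disposition (SAP 10.1).
- *That subtracting years adds about half a year on average to the 3 to 5 years.* The subtraction is only a fallback, and the documents do not show how often it would be needed. The half year arises only against completed age. Against exact age the error averages about zero if birth and consent dates are spread over the year.
- *That negative disease durations would be printed.* The reversed order appears only in a parenthetical example. The general rule beside it does not fix an order, the other interval formulas in the SAP are ordered correctly, and section 11 lists no table of disease duration. It is a slip to correct before anyone programs from it.

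**Conclusion.** The point holds as an undeclared mismatch between protocol and SAP in the reference date of one baseline variable. Reported age exceeds age at treatment start by 3 to about 5 years for every eligible patient. The lower limit rests on the eligibility rule and on consent being the enrolment date. The upper limit rests on the stated maximum observation period and the planned milestones, and would move if enrolment ran late. Where the year-only fallback is used, an individual value can differ from exact age at initiation by as little as about 2 years, through rounding alone.

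It would be wrong to conclude that the annualised relapse rate or any other outcome is affected. The effect stays within the description of the cohort and its prior-DMT subgroups. The correction is worth making because that description is a reported result and the remedy costs almost nothing.

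**What to change.** In SAP 11.1, replace the age variable with age at cladribine initiation, derived as:

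- collected age at consent minus the interval from initiation to consent; or
- initiation year minus birth year if only birth year is held, with a note that the result can be up to a year away from true age.

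Age at consent can stay as a second row with its own label. If the sponsor prefers to report only age at consent, SAP section 7 should list that as a change from the protocol.

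In SAP 9.3, rewrite the example as date of cladribine initiation − date of MS diagnosis + 1.

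The cost is two short edits and one derived variable. The initiation date is already collected, and SAP 11.1 already relies on age or year of birth, so no new data are needed and no information is lost.
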